An adverse event (AE) is defined as any reaction, side effect, or untoward event that occurs during the course of the clinical trial, whether or not it was expected or clinically significant, related or unrelated to vaccination. For this study, AEs will include events reported by the subject, as well as clinically significant abnormal findings on physical examination or laboratory evaluation. A new illness, symptom, sign or clinically significant clinical laboratory abnormality or worsening of a pre-existing condition or abnormality is considered an AE. Stable chronic conditions, such as arthritis, which are present prior to clinical trial entry and do not worsen are not considered AEs.

All AEs occurring during the course of the clinical trial, defined as from the moment of first phlebotomy until study completion, will be collected, documented, and graded by the PI or other investigators. Symptoms present at enrollment will not be classed as AEs, but any new symptoms or signs occurring after this time would constitute adverse events. Specifically vaccine-emergent adverse events occurring during the first 14 days after vaccination will be

collected using a symptom diary. In addition the CRC or designate will maintain telephone contact with the subjects during the 14 days after each vaccination.

XI.2. Serious Adverse Events

The International Conference on Harmonization (ICH) Guideline for Industry: Clinical Safety Data Management: Definitions and Standards for Expedited Reporting, ICH-E2A March 1995 defines serious adverse event (SAE) or reaction as any untoward medical occurrence that:

- results in death;
- is life-threatening; (NOTE: The term "life-threatening" in the definition of "serious" refers to an event in which the patient was at risk of death at the time of the event; it does not refer to an event which hypothetically might have caused death if it were more severe.)
- requires inpatient hospitalization or prolongation of existing hospitalization;
- results in persistent or significant disability/incapacity; or
- is a congenital anomaly/birth defect.

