- is an important medical event that, while none of the above, jeopardizes the subject and may require medical or surgical intervention to prevent one of the outcomes listed above. Examples include allergic bronchospasm requiring intensive treatment in an emergency room or at home, blood dyscrasias or convulsions that do not result in hospitalization, or the development of drug dependency or drug abuse.

An unexpected or unanticipated event involving risks to subjects or others is one that is not described as a risk with respect to nature, severity, or frequency in the protocol and/or informed consent form.

XI.3. Detection of AEs and SAEs

At each visit/assessment, the investigator or research nurse will evaluate AEs. AEs should be solicited until the final study assessment, with particular emphasis on those occurring in the first 14 days after each vaccination. A symptom diary will be given to each participant to complete for 14 days following each dose administration. This will form the basis for AE detection. AEs not previously documented in the study will be recorded in the AE report forms. The nature of each experience, date and time (where appropriate) of onset, outcome, course (i.e. intermittent or constant), maximum intensity, action taken with respect to the study and relationship to any study vaccine should be established.

When an AE or SAE occurs, it is the responsibility of the study investigator to review all documentation relative to the event. The investigator will then record all relevant information regarding an AE/SAE on the Adverse Event form. However, there may be instances when copies of medical records for certain cases are appropriate. In this instance, all subject identifiers will be blinded on the copies of the medical records prior to including the information in the medical record.

XI.4. Evaluation of AEs

The study investigator will attempt to establish a diagnosis of the event based on signs, symptoms, and/or other clinical information. In such cases, the diagnosis should be documented as the AE/SAE and not the individual signs/symptoms. Each adverse event must also be described by its duration (start date, time and duration), an assessment of its cause

(vaccine, coexisting disease, concomitant medication, or others), its relationship to vaccine (not related, unlikely, possibly, probably, definitely), and whether it required specific therapy.

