The investigator will also make an assessment of severity for each AE reported during the study:

- Mild: Self-limiting or minor symptoms that do not affect activities of daily living and do not require treatment.
- Moderate: Symptoms that require treatment in order to carry out activities of daily living.
- Severe: Symptoms preventing activities of daily living and requiring out-patient treatment.

The assessment will be based on the investigator's clinical judgment. An AE that is assessed as severe should not be confused with a serious adverse event (SAE).

XI.5. Follow up of AEs and SAEs

All AEs regardless of severity will be followed by study investigators until satisfactory resolution. The investigator will ensure that follow-up includes any supplemental investigations as may be indicated to elucidate the nature and/or causality of the AE or SAE. This may include additional laboratory tests or investigations, histopathological examinations, or consultation with other health care professionals.

If a study subject withdraws from the study or if an investigator decides to discontinue the subject from the study because of a SAE, the subject must have appropriate follow-up medical monitoring. Monitoring will continue in order to determine whether the problem prompting hospitalization has resolved or stabilized with no further change expected, or is discovered to be clearly unrelated to study drug, or progresses to death. The Investigator/clinical staff will report the follow-up for serious adverse events as noted above.

XI.6. Post-study AEs and SAEs

A post-study AE/SAE is defined as any event that occurs outside of the AE/SAE detection period (ie. after the final Day 84 assessment). Investigators are not obligated to actively seek AEs or SAEs in former study participants. However, if the investigator learns of any SAE, including a death, at any time after a subject has been discharged from the study, and he/she considers the event reasonably related to the study, the investigator will promptly notify any IRB.

XI.7. Reporting of SAEs and Unanticipated Problems

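### The three adverse-event severity definitions in section XI.4 mix effect on daily activities with treatment, so some events fit no grade and an event treated only as an inpatient cannot be Severe

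*Protocol*

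**What the plan says.** Protocol section XI.4 applies the scale to every event: "The investigator will also make an assessment of severity for each AE reported during the study". There are three grades:

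- The lowest is defined by two conditions, one on activities and one on treatment: "Self-limiting or minor symptoms that do not affect activities of daily living and do not require treatment".
- The middle grade links the two and does not limit the kind of treatment: "Moderate: Symptoms that require treatment in order to carry out activities of daily living".
- The top grade again sets two conditions, and here the kind of treatment is named: "Severe: Symptoms preventing activities of daily living and requiring out-patient treatment".

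No rule is given for an event that meets none of these or more than one. The section says only: "The assessment will be based on the investigator's clinical judgment". It warns against confusing severe with serious, so serious events are graded on this scale as well. Whether the event needed treatment is also recorded as a separate item: "whether it required specific therapy".

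Related sections:

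- XI.2 lists, among the criteria for a serious event, one that "requires inpatient hospitalization or prolongation of existing hospitalization".
- VII.3.1 names serious or severe events at least possibly attributable to vaccine among the circumstances in which a subject may be withdrawn.
- VI.6 states that subjects and clinical staff know the allocation; only the immunology staff do not.
- Section V makes description of the adverse-event profile the secondary objective. XII.2 plans numbers and percentages for categorical adverse-event data and a comparison of incidence between doses and vaccines.

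**The concern.** A severity scale that must be applied to every event should give each event one grade and only one. This one cannot, because Mild and Severe each set two conditions, one on activities and one on treatment, and Moderate ties the two together. Combinations outside these pairings have no category. A subject who spends a day in bed without medication is an example.

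The wording of Severe also looks wrong at the top of the scale. It names out-patient treatment only, although the protocol itself foresees hospitalised events.

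Two things are at stake. The first is the severity part of the safety description, in a study that XII.1 says is meant to detect trends in safety. The second is the withdrawal condition in VII.3.1, which uses the severe grade.

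**Working it through.** The protocol states no figure on this point, so there is none to reproduce. The check applies the three definitions literally to a grid.

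**Inputs.** The definitions are those of XI.4. The grid is an assumption of this review: activity effect (none; affected but not prevented; prevented) by treatment needed (none; self-treated; out-patient; inpatient), which gives 3 × 4 = 12 cells. Both conditions in Mild are taken to apply to all symptoms under that grade.

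**Two readings of Moderate.** On the strict reading, Moderate excludes events that prevent activities. On the broad reading, it covers any event with some activity effect for which treatment is needed.

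| Activity effect | Treatment | Strict | Broad |
|---|---|---|---|
| none | none | Mild | Mild |
| none | self-treated | no grade | no grade |
| none | out-patient | no grade | no grade |
| none | inpatient | no grade | no grade |
| affected | none | no grade | no grade |
| affected | self-treated | Moderate | Moderate |
| affected | out-patient | Moderate | Moderate |
| affected | inpatient | Moderate | Moderate |
| prevented | none | no grade | no grade |
| prevented | self-treated | no grade | Moderate |
| prevented | out-patient | Severe | Moderate and Severe |
| prevented | inpatient | no grade | Moderate |

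**Counts.**
- Strict: 3 + 1 + 3 = 7 of 12 cells ungraded, none with two grades.
- Broad: 3 + 1 + 1 = 5 of 12 cells ungraded, and 1 cell with two grades.
- If self-treatment is dropped from the grid, 9 cells remain. The definitions then cover 4 of 9 (strict) or 5 of 9 (broad).

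The cells are not equally likely, so these counts describe the definitions and not how often events will fall in a gap.

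**Ungraded on both readings.** Activities affected without treatment; activities prevented without treatment; treatment required with no effect on activities.

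**Inpatient events.** Where activities are affected but not prevented, the grade is Moderate on both readings. Where they are prevented, there is no grade (strict) or Moderate (broad). Severe is reached on neither reading unless out-patient treatment was also required.

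**Withdrawal condition.** VII.3.1 covers serious or severe events, so a hospitalised event enters it through seriousness. The grading gap therefore matters there for events that are not serious, such as one that prevents activities without out-patient treatment.

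**Weight of one subject.** Moving one subject from one grade to another changes a percentage by 100/n points, with arm sizes from XII.1:
- n = 5 (arms 1 and 2): 100/5 = 20.0
- n = 8 (arms 3 and 4): 100/8 = 12.5
- n = 26 (all randomised): 100/26 = 3.8

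**The case against.** The strongest reply is that little depends on the grade. XII.2 names no severity table and no comparison by severity. Its one stated adverse-event comparison is of incidence, which does not use the grade, and the primary endpoints are immunological. Hospitalised events are recorded as serious, on their own form, and go to the medical monitor under XI.7, so they are not lost from safety reporting. All of this stands, and it limits the size of the point.

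It can also be said that the gaps will seldom be met. IV.4.2 describes local reactions to the inactivated vaccine as mostly mild and rarely interfering with usual activities. IV.3.2 reports no rise in use of concomitant medication after the live vaccine. Mild excludes symptoms that require treatment, so a tablet taken by choice for a trivial symptom may still be Mild. This stands too. A reader might infer from the symptom rates in IV.3.2 (runny nose 44%, headache 40%, tiredness 23%) that ungraded combinations will be common. Those rates say nothing about treatment or activity limitation, so they do not show it.

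The third reply is that clinical judgment fills the gaps. It helps in choosing between categories whose boundaries are known, but it gives no common rule where no definition applies or two do. Knowledge of the arm would remain under any scale, so rewording would remove the lack of a rule and not the open-label grading.

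**Conclusion.** The point holds in a limited form. The definitions in XI.4 are not exhaustive on either reading, overlap in one cell on the broad reading, and do not let an event treated only as an inpatient reach Severe. This is a defect in a rule that the protocol itself fixes and that investigators apply when data are collected. It is not a detail left to a later analysis plan.

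The effect is confined to the descriptive secondary safety profile and the use of Severe in VII.3.1. One regraded subject is worth 20.0 or 12.5 percentage points within an arm and 3.8 points overall. Adverse-event incidence and the primary endpoints are unaffected.

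Two stronger readings are not supported. A reader might infer that every inpatient event is left without a grade. Moderate does not restrict the type of treatment, so some inpatient events are Moderate on either reading. A reader might also infer that a planned between-arm severity analysis is compromised, but the protocol plans none by name. A severity summary is only a plausible part of the adverse-event profile.

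The conclusion rests on a literal reading of the three definitions and on the assumed grid. The protocol gives no figures for how often events would fall in the gaps.

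**What to change.** Reconcile the XI.4 definitions with XI.2 and VII.3.1 so that every adverse event, including a hospitalised one, falls in exactly one grade. One way is to grade on a single axis and report treatment from the therapy item that XI.4 already records. Because the severe grade also appears in VII.3.1, those responsible for the clinical rule should settle the two sections together. This review does not say where the boundary of Severe should lie or what the withdrawal condition should be.

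For events already graded, state in the report how those that fitted no definition, or more than one, were handled. Regrading them from recorded data should not be assumed possible: the items listed in XI.3 and XI.4 include therapy and maximum intensity but no separate item for effect on activities. Any regrading now would also be retrospective and done with knowledge of the arm.

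The cost is a wording change in the protocol, with a matching change to the adverse-event form if needed. The downside is that grades assigned under the new wording may not be directly comparable with those already assigned.

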Each of the reassortment strains is inoculated into specific pathogen-free eggs and incubated to allow viral replication. The monovalent bulk is then harvested, filtered and combined to form trivalent vaccine. Each pre-filled sprayer contains a single 0.2ml dose. Each dose contains 10FFU (fluorescent focus units) of live attenuated influenza virus reassortments of each of the 3 strains (for the 2008/9 Northern Hemisphere season these will be: an A/Brisbane/59/2007 (H1N1)-like virus, an A/Brisbane/10/2007 (H3N2)-like virus, and a B/Florida/4/2006-like virus), monosodium glutamate, hydrolyzed porcine gelatin, arginine, sucrose, dibasic potassium phosphate, monosodium phosphate, and <0.015mcg gentamicin sulphate. There are no preservatives.

IV.3.2. Safety and tolerability following single and dual dose administration in healthy subjects

Pre-licensure clinical trials, in which more than 20,000 subjects (of whom 3,700 were healthy adults) received more than 28,000 doses of LAIV (FluMist®), showed the vaccine to be safe and well-tolerated (Belshe 2004). In the largest published study of safety in healthy adult volunteers, a randomized double-blind, placebo-controlled trial of LAIV, the following AEs were reported following a single dose of vaccine: runny nose 44%; sore throat 27%; fever 1%; cough 17%; headache 40%; muscle aches 19%; tiredness 23%. Most of these AEs were reported equally between the LAIV and placebo groups; however runny nose and sore throat were significantly more likely to be reported in the LAIV group (17% and 10% increase respectively) (Nichol 1999). Most vaccine-related AEs lasted just 1-2 days and occurred during the first 7 days after vaccination. There was no increase in use of concomitant medications such as antibiotics or cold remedies in LAIV recipients. There were no SAEs attributable to LAIV.

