- Arm 3: FluMist® live intranasal vaccine 0.2mL (0.1mL per nostril) single dose, then Fluzone® influenza virus vaccine 0.5mL intramuscularly single dose 8 weeks (±7 days) later (LAIV then IIV).
- Arm 4: Fluzone® influenza virus vaccine 0.5mL intramuscularly single dose, then FluMist® live intranasal vaccine 0.2 mL(1mL per nostril)single dose 8 weeks (± 7 days) later (IIV then LAIV).

VI.8. Packaging, Labeling and Storage of Vaccines

| Chemical name: | N/A | |
|--|---|--|
| Generic name: | FluMist® Influenza Virus Vaccine Live, Intranasal | |
| Trade name: FluMist® | | |
| Dosage form:0.2mL pre-filled, single-use nasal spray | | |
| Strength: | Each 0.2mL dose contains 10 ^{6.5-7.5} FFU (fluorescent focus units) of live attenuated influenza virus reassortments of each of the 3 strains for the 2009/2010 season A/South Dakota/6/2007 (H1N1) (an A/Brisbane/59/2007-like), A/Uruguay/716/2007 (H3N2) (an A/Brisbane/10/2007-like), and B/Brisbane/60/2008. | |
| Manufacturer: | MedImmune Vaccines Inc., Gaithersburg, MD 20878 | |
| Source: | Donated by MedImmune | |
| Storage: | 2-8°C | |

VI.8.2. Inactivated Influenza Vaccine

| Chemical name: | N/A |
|----------------|---|
| Generic name: | Influenza Virus Vaccine |
| Trade name: | Fluzone® |
| Dosage form: | 0.5ml pre-filled syringe |
| Strength: | Each 0.5ml dose contains 45 micrograms of hemagglutanin in the recommended ratio of 15 micrograms each, representative of the following 3 prototype strains for the 2009/2010 season: A/Brisbane/59/2007, IVR-148 (H1N1), A/Uruguay/716/2007, NYMC X-175C (an A/Brisbane/10/2007-like strain) (H3N2), and B/Brisbane/60/2008. |
| Manufacturer: | Sanofi Pasteur Inc., Swiftwater, PA 18370 |
| Source: | Thailand purchase |
| Storage: | 2-8°C |

VI.9. Duration of Subject Participation

This study will take up to 12 months from enrollment of the first subject to completion of the *in vivo* portion. Each subject will be followed up for approximately 12 weeks following entry into the study (screening, dosing, follow-up). The total study duration will be 5 years.

A subset of previously enrolled subjects may be invited to participate in an additional phase of the study, which will involve consent for use of stored sample and a possible single blood draw if extra sample is required. No follow-up will be required after the day of blood draw

VI.10. Procedures

VI.10.1. In vivo Procedures

VI.10.1.1. Informed Consent Process

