Potential subjects will have the study explained in detail during a PowerPoint presentation. The informed consent process will take place before any other study procedures and a unique identification number will be assigned. After review the subject will be asked to sign the consent form. Two copies of the consent form should be completed (or the original photocopied) so that the subject can get a copy and the original copy will be kept for the study records. All volunteers will be recorded in a screening log (see Section XIV.2) and those who are subsequently enrolled will be noted with a subject number.

VI.10.1.2. Pre-Study Screening

The pre-study screening visit may be performed anytime within 30 days of planned dosing. The screening examination will consist of:

- Demographic details.
- Medical history to include medical and surgical history, vaccination history and smoking history.
- Physical examination including vital signs (BP, HR, RR, temp), height and weight.
- Blood draw for CBC and HIV test (3ml).

[figure not shown]
The HIV testing will be done by Department of Retrovirology, AFRIMS as follows:

| Test | Screening Test | Confirmatory Test |
|-------|-----------------------------------|---------------------------------------|
| HIV-1 | GS rLAV HIV-1 EIA (RET-GL-115) | GS HIV-1 Western Blot (RET-GL-127) |

Pre- and post- HIV test counseling will be given and, if the subject wishes, referral to a specialist recommended by the US Embassy Medical Unit will be made for subjects testing positive. Subjects may choose not to be informed of their HIV test result and in such a case will simply be told that they do not fulfill all the criteria for enrollment. HIV testing may be waived in subjects who have had a negative HIV test result within 2 months of screening.

Subjects should fulfill inclusion criteria outlined in Section VII.1 and not have any of the exclusion criteria listed in Section VII.2

VI.10.1.3. Scheduled Visits

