Day 0: The subject will attend for the first dose of vaccine. The study procedures will be reviewed and informed consent re-affirmed verbally. The continued good health of each subject will be confirmed by review of the subject's medical and medication history, medical, surgical and social history, and a brief targeted examination including vital signs (BP, HR, RR and temp). A baseline venous blood sample will be collected (60ml for measurement of cells; 10ml for serum for immunology assay) and a nasal wash for baseline secretory antibody measurements performed. A urine pregnancy test will be performed on females of child-bearing age. If the screening test results (CBC and HIV test) are within normal limits and the subject is not pregnant, the subject will be assigned next available randomization number with details of the vaccine regimen contained within a sealed envelope with that randomization number written on it (see Section VI.6).

The first dose of intranasal FluMist® or intramuscular Fluzone® will then be given and the exact time noted. Following dosing, the clinical staff will inspect the spray container or syringe to confirm that the full dose was delivered. The subject will remain under observation from this time until 30 minutes later to ensure there are no early adverse events. They will then be allowed to return home. Subjects will keep a symptom diary for 14 days following administration of the vaccine.

Day 14 (-2 to +3 days): The subject will attend for symptom diary review and vital signs. 70ml blood will be collected (60ml for measurement of cells and 10ml for serum for immunology assay from a venous sample. A nasal wash will be performed.

Day 28 (-2 to +3 days): All subjects will attend for interim history, and vital signs review. 10ml venous blood will be collected for serum for immunology assay. A nasal wash will be performed.

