VI.12. Accountability Procedures

The Drug Accountability Form will be updated each time a subject receives a dose of vaccine. The form will record the following information for each dose of vaccine: name of vaccine, date administered, subject number and randomization code, number of doses of vaccine at start of study, number of doses of vaccine remaining, signature.

VI.13. Maintenance of Randomization Codes and Procedures for Breaking Codes

This is an open-label study. However all samples for analysis will be coded and assays completed with laboratory technicians blinded as to the randomization sequence. Therefore it is not anticipated that the randomization code will need to be broken until the end of the study for analysis purposes.

VII. SELECTION AND WITHDRAWAL OF SUBJECTS

VII.1. Subject Inclusion Criteria

- 1. Aged 18-49 years.
- 2. Healthy as determined by the PI or designate
- 3. Willing to give informed consent.
- 4. Willing to attend follow-up appointments and undergo study procedures.
- 5. US passport holder residing in Bangkok
- 6. If military, have a letter of approval for participation from the chain of command (Unit Commander).

VII.2. Subject Exclusion Criteria

- 1. History of hypersensitivity to eggs, egg proteins, gentamicin, gelatin or arginine.
- 2. Severe or life-threatening reaction to any previous vaccine.

3. History of chronic respiratory illness, including asthma and sinusitis that in the opinion of the investigator warrants exclusion.

- 4. History of heart disease that in the opinion of the investigator warrants exclusion
- 5. History of kidney disease that in the opinion of the investigator warrants exclusion
- 6. Metabolic disease such as diabetes
- 7. Immunocompromised as determined by the PI, or a household contact of an immunocompromised individual.
- 8. History of Guillain-Barre syndrome.

9. Blood disease including sickle cell disease and/or bleeding tendency (by history or based on medical records).

10. Any influenza vaccination within 6 months prior to enrollment, or any other vaccine within 30 days of either dose of influenza vaccine.

11. Pregnant woman or nursing mother or unwilling to use reliable contraception during the study period until the final day of follow-up.

12. Blood donation within the preceding 3 months, or screening hemoglobin value of <12.5 g/dl. (males) or <11.6 g/dL (females).

Receipt of blood products including immunoglobulins within the preceding 3 months.

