In addition there will be an in-house study monitor assigned to this study to ensure compliance with GCP/ICH standards. Monitoring will consist of a pre-study site visit, regular monitoring visits and a post-study visit.

XII. STATISTICAL METHODS

XII.1. Sample Size and Power

This is a descriptive study designed to detect trends in safety and immune responses that would warrant expanded investigations of potentially promising combinations {Lancaster, 2004} {Browne, 1995}. The sample size of 8 subjects in arms 3 and 4 and 5 in arms 1 and 2 is in the range of what is considered adequate for phase I trails and is not based on sample size and power calculations {Stephenson, 2005} {Lin, 2006} {Nicholson, 2001}.

Recruitment of subjects is likely to be affected by the limited number of US citizens resident in Bangkok who fulfill the eligibility criteria. Hence there will be no stratification of enrolment based on gender; this and other possible confounders (such as prior receipt of influenza vaccines) can be addressed in future large-scale trials.

XII.2. Study Outcome Analysis

Primary Analysis

Immunological data and other continuous variables will be expressed as geometric means and standard deviations if the data are normally distributed, and the vaccine groups compared using parametric tests. If not normally distributed they will be expressed as medians and the range and interquartile range given; comparison between groups will then be by non-parametric tests.

Secondary Analyses

In vivo (AE) data will be analyzed as follows: categorical data will be presented using counts and percentages, whilst continuous variables will be presented using the mean, (standard deviation) or median (range and interquartile range), and number of subjects. Percentages will be rounded to a maximum of one decimal place. All statistical tests will be performed using a 5% significance level, leading to 95% confidence intervals. Differences in incidence of reported AEs between doses and vaccines will be determined. Statistical analyses will be carried out in-house using Stata 10.0 (College Station, Texas).

XIII. ETHICAL CONSIDERATIONS

XIII.1. Study Approval

Scientific approval for this study will be obtained from the Scientific Review Committee at AFRIMS. Ethical approval will be sought from the WRAIR IRB (FWA 00000015) and the USAMRMC ORP HRPO. This study will be governed by ICH GCP guidelines.

XIII.2. Risks and Benefits of Participating

Benefits

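### The stated between-arm comparison does not carry in the Day 0 titre, and prior influenza vaccination is put off to later trials, although both are already collected; adjusting for Day 0 would be a nearly free improvement

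*Protocol*

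**What the plan says.** **Analysis.** Protocol XII.2 (Primary Analysis) summarises the immunological data and compares the vaccine groups by parametric tests, or by non-parametric tests if the data are not normally distributed. It names no covariate and does not say whether the quantity compared is the post-dose titre or the change from Day 0.

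**Confounders.** XII.1 explains that recruitment limits rule out stratifying enrolment by gender, and continues that "this and other possible confounders (such as prior receipt of influenza vaccines) can be addressed in future large-scale trials".

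**Baseline.** The Study Summary (Study Design and Methodology) says that responses after each dose are compared with baseline values, and the primary endpoints are pre- and post-vaccination responses.

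**Data collected.** Screening (VI.10.1.2) includes "Medical history to include medical and surgical history, vaccination history and smoking history". On Day 0 (VI.10.1.3), "A baseline venous blood sample will be collected", together with a nasal wash, before dose 1.

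**Who can enter.** VII.2 excludes "Any influenza vaccination within 6 months prior to enrollment", so someone vaccinated in the previous season can be eligible.

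**Strains.** Section IV.3.1 states that "for the 2008/9 Northern Hemisphere season these will be: an A/Brisbane/59/2007 (H1N1)-like virus", with an A/Brisbane/10/2007-like H3N2. Section VI.8 gives the 2009/10 FluMist H1N1 component as "A/South Dakota/6/2007 (H1N1) (an A/Brisbane/59/2007-like") and the H3N2 component as A/Brisbane/10/2007-like. The B component differs between the two seasons.

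**Size.** XII.1: "The sample size of 8 subjects in arms 3 and 4 and 5 in arms 1 and 2"; this "is not based on sample size and power calculations".

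**The concern.** Recruitment limits are a fair reason not to stratify enrolment. They are no reason to leave a recorded prognostic variable out of the analysis, since adjustment needs no further subjects. By the protocol's own strain lists, a volunteer vaccinated in 2008/9 has already met both influenza A components of the study vaccines, so for that person the study prime may act as a boost. Section IV.2.4 refers to step-wise increasing antibody responses to repeated doses of inactivated vaccine. Section IV.2.4 and IV.2.6 aside, section IV.6 notes that both vaccines contain N1, the neuraminidase subtype of H5N1, so earlier seasonal vaccination could plausibly also bear on the cross-reactivity endpoints.

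At stake is the first primary objective, whether a prime-boost strategy augments cross-reactivity, and the choice of combinations for larger studies, which XII.1 gives as the purpose of the trial. If one arm happens to start with higher titres, an unadjusted comparison cannot separate that head start from the regimen, and it is usually less precise than it could be.

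**Working it through.** The protocol makes no power calculation, so there is no figure of that kind to reproduce. Its counts agree: 5 + 5 + 8 + 8 = 26 randomised, and 26 + 8 = 34 recruited. The arm sizes and the 5% level come from section XII. SDs, correlations, vaccination rates and the 1.5 SD effect below are assumptions, shown over ranges.

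**1. Chance imbalance in Day 0 titre.** For arms of n1 and n2, SE = SD × √(1/n1 + 1/n2). A 2-fold difference in geometric mean titre is 1 on the log2 scale.
- 8 v 5, SD 1.5: SE = 1.5 × √(1/8 + 1/5) = 0.855; P(|difference| ≥ 1) = 2 × [1 − Φ(1/0.855)] = 0.242.
- 8 v 5, SD 2.0: SE = 1.140; probability 0.380.
- 8 v 8: SE 0.750 and 1.000; probability 0.182 and 0.317.

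**2. Chance imbalance in prior vaccination.** Exact binomial, assumed rate 30%, 50% or 70% of volunteers:

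| Arms | Gap ≥ 30 points | Gap ≥ 40 points |
|---|---|---|
| 8 v 5 | 27–35% | 13–18% |
| 8 v 8 | 17–21% | 5–8% |
| 5 v 5 | 30–34% | 30–34% |

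(With 5 per arm gaps move in steps of 20 points, so the two columns agree.) By simulation, at least one pair of the four arms differs by 40 points or more in 48–56% of trials.

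**3. What imbalance does to the unadjusted test.** Simulation with normal log titres, no regimen effect, two-sided 5%, Day 0/post correlation ρ from 0.3 to 0.8. Over all trials the t-test on post-dose titre rejects in 4.8–5.2%, so overall error is held. Among trials where the Day 0 means differ by at least 0.75 SD (about 19% of 8 v 5 comparisons, 13% of 8 v 8), false positives are:

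| Analysis | 8 v 5 | 8 v 8 |
|---|---|---|
| Post-dose titre, ρ 0.3 to 0.8 | 7% to 18% | 7% to 23% |
| Change from Day 0, ρ 0.3 to 0.8 | 12% down to 7% | 15% down to 8% |
| ANCOVA on Day 0 | about 5% | about 5% |

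Comparing change scores therefore lessens the problem only when the correlation is high.

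**4. Precision.** Relative to the post-dose titre alone, the large-sample variance of the arm difference is 1 − ρ² for ANCOVA and 2 − 2ρ for change:
- ρ 0.3: 0.91 and 1.40
- ρ 0.5: 0.75 and 1.00
- ρ 0.7: 0.51 and 0.60
- ρ 0.8: 0.36 and 0.40

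For a true difference of 1.5 SD, simulated power for 8 v 5 goes from 66% unadjusted to 74% (ρ 0.5) or 88% (ρ 0.7); for 8 v 8, from 80% to 87% or 96%. At ρ 0.3 there is no gain over the post-dose titre.

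**5. Cost.** Four arms and one covariate leave 26 − 4 − 1 = 21 residual degrees of freedom.

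**The case against.** The strongest reply is that covariates are usually settled in a statistical analysis plan, which is not at hand, and that nothing in XII.2 forbids adjustment. That is right as far as silence goes. But the deferral of prior vaccination in XII.1 is a stated choice, and XII.2 describes the primary comparison without baseline, so the protocol text can be improved as it stands.

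A reader might infer that the Day 0 titre is ignored altogether. The Study Summary does not support this: responses are compared with baseline. The gap is only in how baseline enters the comparison between arms.

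A reader might also infer that imbalance will pass for a regimen effect, or biases the trial. Allocation is randomised and overall error stays near 5%; the risk is conditional on the imbalance that occurs.

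Nor do the documents support calling prior vaccination the main explanation of any H5N1 cross-reactivity. The shared strains are human H1N1 and H3N2. The common N1 subtype makes a link plausible, but no size is given.

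Two technical points stand. The variance saving is largest against the post-dose titre alone: if arms were compared on change, the ratio at ρ 0.7 would be 0.51/0.60 = 0.85. And negative sera in the microneutralization assay are assigned a titre of 10 (VI.10.2.4); if most Day 0 H5N1 values lie there, the covariate carries little information and the assumed SDs and correlations do not apply.

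Finally, the trial calls itself descriptive and a pilot, and openly names the confounder.

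**Conclusion.** The point holds as an improvement that should be made, not as a flaw that invalidates the trial. The stated between-arm comparison is unadjusted, and a recorded confounder is put off to later studies although it can be examined here. In arms of 5 and 8, a 2-fold or larger gap in Day 0 geometric mean titre between an arm of 8 and an arm of 5 has probability 24–38%, given log2 SDs of 1.5–2.0. The consequence is lost precision and a result that may mislead in the realised trial, with overall type I error still near 5%. The gain from adjustment rests on the Day 0/post correlation: useful at 0.5 or above, little or none at about 0.3 or lower. It will differ by assay.

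**What to change.** - **XII.2:** compare arms on log titre at each post-dose visit by ANCOVA, with the same subject's Day 0 log titre (same assay, strain and specimen) as covariate. Where the non-parametric branch applies, use a rank-based ANCOVA.
- **Assay floor:** where most Day 0 values sit at the floor, as may happen with H5N1 microneutralization at titre 10, report the unadjusted comparison.
- **Prior vaccination:** tabulate prior-season influenza vaccination by arm and use it only as a sensitivity covariate; 26 subjects will not carry more.
- **XII.1:** keep the statement that enrolment is not stratified, but reword the sentence so that it no longer implies prior vaccination cannot be examined in this trial.
- **Day 56 titre:** do not adjust between-arm comparisons for it. It is measured after the randomised first dose; use it only descriptively, for within-subject change after dose 2.
- **Timing:** section IV.7 reports a preliminary analysis of the data, so label the adjusted analysis with the date it was specified.

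The cost is wording, a little more analysis and one degree of freedom (21 residual). No new samples or visits are needed.
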